**Study Plan/SAP**

1. Title, academic degree, name and surname, and place of employment of the applicant:

*Dr hab. n. med. [name]  
Uniwersyteckie Centrum Rehabilitacji (UCR)  
[name]*

2. [contact]**

3. Name of the organizational unit of the Wroclaw Medical University implementing the project:

*Uniwersyteckie Centrum Rehabilitacji – place of data collection and analysis  
USK - Szpital Tymczasowy na [name] - place of surveys; possibly additional centers after their authorities' decision that will not impact study design (only for Team members).*

4. Project title: **Physical Activity and the Course of COVID-19.**

*- in hospitalized patients*

5. Registration number of the Center for the Support of Science of the Wroclaw Medical University - **none**

6. Detailed description of the project together with justification of its purposefulness and feasibility assessment:

*Physical activity is one of the factors modulating human immunity and affecting general efficiency, including respiratory one. For this reason, its level may be associated with the severity of the course of COVID-19.*

*The study aims to assess the relationship between physical activity levels before the onset of COVID-19 and the course of the disease. The course of the disease is often surprising and independent of selected poor prognostic factors; therefore, it is advisable to look for relationships between those variables that have not yet been analyzed.*

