**Methodology:**

*The study consists of a survey on physical activity prior to contracting COVID-19 among patients hospitalized due to this disease at the USK (Temporary Hospital for COVID patients).*

*Time Frame: 01 Nov 2021- throughout the entire period of hospital activity*

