**Inclusion criteria:**

- *adult*
- *sex – any*
- *race – any*
- *confirmed COVID-19 infection and hospitalization in the COVID-19 treatment unit*

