**Exclusion criteria:**

- pregnancy;*
- inability to complete the questionnaire during hospitalization or up to a week after discharge;*
- history of a significant cardiovascular event in the last 6 months (acute coronary syndrome, stroke, amputation, revascularization of peripheral vessels, pulmonary or peripheral embolism of any etiology) if the patient did not complete the rehabilitation process;*
- symptomatic chronic respiratory disease not responding to therapy before hospitalization for COVID-19 (or no therapy);*
- any dyspnea at rest in the last month before COVID-19;*
- injury to the locomotor system in the last month before contracting COVID-19;*
- hospitalization in the last month before contracting COVID-19.*

*In order to describe the group and analyze the survey results, information from the patient's interview, physical examination, and the results of basic and additional tests contained in the patient's hospital documentation during the stay due to COVID-19 will be used.*

*The International Physical Activity Questionnaire (IPAQ) short form will be used to determine the level of physical activity.*

*After consenting to participate in the study, the patient will be asked to answer 7 survey questions. If the patient's condition prevents participation in the survey, the patient will be allowed to participate on a different day, including within 7 days from discharge, or indicate a relative who can fill out the survey for the patient.*

*Each patient will be given an identification number, and the list of participants will be prepared.*

*Data from medical records will be prospectively collected for Primary Outcome Measures: death due to COVID-19, recovery – patients discharged home, transfer to intensive care unit (ICU), and Secondary Outcome Measures: hospitalization length before transfer to intensive care unit, laboratory tests. Additional data – lab results, comorbidities, pharmacotherapy history, and complications related to hospitalization – will be collected if available.*

*Then, they will be combined with the IPAQ results (the surveys will be analyzed anonymously, and paper version of IPAQs will be archived in Uniwersyteckie Centrum Rehabilitacji, [name]) in one document (Excel, based on the patient number).*

*Data ready for statistical analysis will be sent to a statistician and analyzed according to the Statistical Analysis Plan (SAP).*

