## Statistical Analysis Plan

Sample size calculation for confidence interval: 95%; fraction size: 0.5; max error: 5%: 384 participants.

The variables subjected to statistical analysis will be on nominal scales – including dichotomous ones – and ratio scales:

- variables expected in the ratio scales: raw MET, hospitalization length, age, BMI, and concentration levels of all biochemical factors studied;

- variables expected in dichotomous scales: sex, oxygen therapy need (Yes/No), information about patient death or transfer, information about complications, variables describing the study group in terms of history and comorbidities, and medication groups.

The variables in the interval scales are nicotine addiction and IPAQ level (the latter will be treated as a directional, three-item interval variable).

Statistical analysis will begin by verifying the accuracy of the data contained in the compiled database. For this purpose, descriptive statistics with histograms will be determined for ratio variables and tables of sample sizes for nominal variables. Then all extreme outliers and dubious results will be verified again with the source materials. Gaps found in the database will not be replaced with any other values.

In the case of variables on ratio scales, their normality of distribution will be assessed. The Shapiro-Wilk W test will determine the normality of distribution. Characterization of this group of variables will be based on the statistical significance of the W-test. The following descriptive statistics will be defined for variables with a normal distribution: size, mean value, standard deviation, and 95% confidence interval for the mean value. While size, median, and range will be determined for variables that are not normally distributed.

The Shapiro-Wilk W test with a significance level of  $\alpha=0.05$  will be used to evaluate the normality of distributions.

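### COVID-19 vaccination status is neither a named data item nor part of any analysis, so the plan as written does not provide for separating it from physical activity

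*Combined protocol and SAP*

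**What the plan says.** The opening project description gives the aim: "The study aims to assess the relationship between physical activity levels before the onset of COVID-19 and the course of the disease". Activity is measured by questionnaire and nothing is randomised.

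The Methodology section sets the period: "Time Frame: 01 Nov 2021- throughout the entire period of hospital activity". The disease-related inclusion criterion is "confirmed COVID-19 infection and hospitalization in the COVID-19 treatment unit". No inclusion or exclusion criterion refers to vaccination.

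The data to be collected are described in the paragraphs after the exclusion criteria. A general clause draws on "information from the patient's interview, physical examination, and the results of basic and additional tests contained in the patient's hospital documentation". After the primary and secondary outcomes, a further sentence reads "Additional data – lab results, comorbidities, pharmacotherapy history, and complications related to hospitalization – will be collected if available".

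The SAP lists its ratio-scale variables as "raw MET, hospitalization length, age, BMI, and concentration levels of all biochemical factors studied". Its dichotomous variables include sex, oxygen therapy, death or transfer, complications, and "variables describing the study group in terms of history and comorbidities, and medication groups". Nicotine addiction and IPAQ level are listed separately. Missing values are to be left as they are.

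The analyses are principal components, correlations, chi-squared tests with 2x2 odds ratios, group comparisons, and a Cox model for the effect of the IPAQ value on survival. No adjustment covariate or stratification factor is named for any of them.

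**The concern.** In a non-randomised cohort, a difference in outcome between activity levels can arise from anything that differs between those levels and also bears on outcome. Vaccination before infection is an obvious candidate for a cohort enrolled from November 2021. This rests on general subject knowledge: the documents state neither that vaccines were available to these patients nor what effect they had.

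The study's justification says the findings may help plan prevention and gauge the prognostic effect of behaviour. That is close to a causal use, and it needs the main competing preventive exposure to be on record. If vaccination is not recorded uniformly, a protective, null or adverse association with activity would each have a rival explanation that could not be examined. The investigators could not even check whether vaccination differs by activity level.

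The gap is related to the SAP's lack of any adjusted analysis but is not the same. Age, BMI and comorbidity are at least listed, so a later analyst could adjust for them. Vaccination is not assured even to that extent.

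**Working it through.** **The plan's own figure.** The SAP's sample size follows from n = z²p(1−p)/e² with z = 1.96, p = 0.5 and e = 0.05: 3.8416 × 0.25 / 0.0025 = 384.16, which agrees with the stated 384. The present point does not change it.

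**Where vaccination could appear.**

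| Place | Nearest wording | Vaccination named? |
|---|---|---|
| Inclusion and exclusion criteria | none | no |
| General source clause | interview, examination, test results | no |
| Additional-data sentence | drug history, comorbidities | no; collected only if available |
| SAP ratio variables | none | no |
| SAP dichotomous variables | history, medication groups | no |
| SAP tests and models | IPAQ value only in the Cox model | no |

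**How large the confounding could be.** All inputs below are assumptions, because the documents give none:
- no true effect of activity;
- mortality of 15% in unvaccinated patients;
- in-hospital risk ratio r for vaccinated against unvaccinated patients;
- vaccinated share v in each activity group.

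Group risk = 0.15 × [(1 − v) + r·v]. The unadjusted odds ratio (OR) compares active with inactive patients. Swapping the two shares inverts it.

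| r | v active / inactive | Risk active | Risk inactive | OR | OR with shares swapped |
|---|---|---|---|---|---|
| 0.5 | 50% / 40% | 0.1125 | 0.120 | 0.93 | 1.08 |
| 0.5 | 60% / 40% | 0.105 | 0.120 | 0.86 | 1.16 |
| 0.3 | 60% / 40% | 0.087 | 0.108 | 0.79 | 1.27 |
| 0.3 | 70% / 40% | 0.0765 | 0.108 | 0.68 | 1.46 |
| any | equal | equal | equal | 1.00 | 1.00 |

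First row in full: (0.1125/0.8875) / (0.120/0.880) = 0.1268/0.1364 = 0.93.

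**Sensitivity to the assumptions.** With 20% mortality if unvaccinated and shares of 50% and 30%, r = 0.3, 0.5 and 0.7 give ORs of 0.80, 0.86 and 0.92. Shares of 60% and 30% give 0.70, 0.80 and 0.88. The bias shrinks as r approaches 1 and vanishes when uptake is equal.

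**Scale against sampling error.** Suppose 384 patients fall into two equal groups of 192, with risks of 10.5% and 12%. Expected deaths are 20.16 and 23.04. The standard error of the log OR is √(1/20.16 + 1/171.84 + 1/23.04 + 1/168.96) = 0.324. The 95% interval around 0.86 is exp(−0.150 ± 1.96 × 0.324), or about 0.46 to 1.62.

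**The case against.** The strongest reply is that absence from one sentence does not show that an item will not be collected. The additional-data sentence is not exhaustive: BMI, nicotine addiction and oxygen therapy are missing from it, yet all three are SAP variables. The plan works in categories and names no single comorbidity or drug class. A clinician taking a history in this setting might well record vaccination. This stands. A reader might infer that vaccination will not be collected, or that its effect can never be separated from that of activity. The documents support only that it is not named and therefore not assured.

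A second reply is that the item may be recoverable, because records are linked to the questionnaire by patient number. This also stands where the record notes vaccination, so the omission should not be called irreversible. It does not ensure uniform status and dates.

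Third, a reader might infer that vaccination is shown to affect every primary outcome, or that the bias must flatter activity. The documents state neither. Bias needs vaccination to be related both to activity and to outcome among patients already admitted, and its direction is unknown.

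Fourth, the moderate scenarios lie well inside sampling error at this sample size. That is true of any single result. It does not remove the bias from the point estimate, and it gives no reason to leave a cheap field unrecorded.

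Finally, recording vaccination alone would not cure the analysis. A table split by vaccinated yes/no would remain confounded by age and comorbidity, and it would be sparse. At an assumed 12% mortality, 384 × 0.12 ≈ 46 deaths spread over three IPAQ levels and two strata average fewer than 8 per cell. This is accepted and shapes the fix.

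**Conclusion.** The concern holds in a limited form. In the text available for review, vaccination status is not a named data item, not an SAP variable and not part of any analysis, while enrolment is open-ended from November 2021 and ignores it. General wording might capture it, but nothing commits to that. The plan as written therefore does not provide for separating vaccination from activity.

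On the main illustrative assumptions, the distortion in the odds ratio for death lies between 0.68 and 0.93 in one direction and between about 1.08 and 1.46 in the other, with none if uptake is equal. The extremes need a 30-point uptake gap together with a risk ratio of 0.3. The true gap and the true risk ratio cannot be obtained from the documents, so these figures show what is possible and do not estimate what will occur.

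**What to change.** **Data collection (paragraphs after the exclusion criteria).** Make vaccination status before admission a required item: none, incomplete, or complete or boosted, with the date of the last dose where known. Take it from the interview or hospital record. For patients already enrolled, back-fill it from the record, and code it as unknown where the record is silent.

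**SAP.** List vaccination status as a variable and tabulate it by IPAQ level. Include it with age and comorbidity as a covariate in the Cox model and in an adjusted logistic model for death and for ICU transfer. Keep any vaccination-stratified table as descriptive only. With perhaps 46 deaths the covariate list must stay short, so fix in advance how vaccination and comorbidity will be coded.

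**Cost.** One extra field from sources already in use, some unknown statuses, and slightly wider intervals for the activity effect. The stated 384 and patient care are unaffected.

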*There is no information in the literature on the impact of daily physical activity (obtained directly from patient questionnaires) on the course of COVID-19. Learning what relationships (if any) exist between them can help plan the prevention of this infectious disease and assess the strength of behavioral actions with their impact on the prognosis.*

Additional documents (underline as appropriate)

- a copy of the Rector's decision to grant funding as part of the statutory activities of the University
- information for persons participating in a medical experiment containing detailed data on the purposes and principles of conducting the research, expected therapeutic and other benefits for these persons, and the risk associated with participation;
- a written commitment signed by the researcher to obtain informed consent from all test subjects or their legal representatives;
- a template of the patient's or their legal representative's consent form, which contains statements regarding:
  - voluntary consent to participate in the medical experiment after reading the information,
  - confirmation of the right to ask the researcher questions and receive answers to these questions,
  - information about the possibility of withdrawing from participation in the study at any stage;
- information on the method of collecting and processing personal data for the person participating in a medical experiment;
- research insurance information;
- consent of the person participating in a medical experiment or their legal representative to the processing of data relevant to participation.
- consent of the Head of the USK Temporary COVID Hospital/s (available at the Bioethics Committee office)
- IPAQ – polish version-  
[https://www.academia.edu/19229070/Mi%C4%99dzynarodowy\\_Kwestionariusz\\_Aktywno%C5%9Bci\\_Fizycznej\\_IPAQ\\_wersja\\_polska](https://www.academia.edu/19229070/Mi%C4%99dzynarodowy_Kwestionariusz_Aktywno%C5%9Bci_Fizycznej_IPAQ_wersja_polska)

Head  
of the organizational unit  
implementing the project

.....  
Signature, stamp

Applicant

.....  
Signature, stamp

Wrocław, .....

---

References:

Brodin P. Immune determinants of COVID-19 disease presentation and severity. *Nat Med.* 2021 Jan;27(1):28-33. doi: 10.1038/s41591-020-01202-8. Epub 2021 Jan 13. PubMed ID: 33442016

## Statistical Analysis Plan

Sample size calculation for confidence interval: 95%; fraction size: 0.5; max error: 5%: 384 participants.

The variables subjected to statistical analysis will be on nominal scales – including dichotomous ones – and ratio scales:

- variables expected in the ratio scales: raw MET, hospitalization length, age, BMI, and concentration levels of all biochemical factors studied;

- variables expected in dichotomous scales: sex, oxygen therapy need (Yes/No), information about patient death or transfer, information about complications, variables describing the study group in terms of history and comorbidities, and medication groups.

The variables in the interval scales are nicotine addiction and IPAQ level (the latter will be treated as a directional, three-item interval variable).

Statistical analysis will begin by verifying the accuracy of the data contained in the compiled database. For this purpose, descriptive statistics with histograms will be determined for ratio variables and tables of sample sizes for nominal variables. Then all extreme outliers and dubious results will be verified again with the source materials. Gaps found in the database will not be replaced with any other values.

In the case of variables on ratio scales, their normality of distribution will be assessed. The Shapiro-Wilk W test will determine the normality of distribution. Characterization of this group of variables will be based on the statistical significance of the W-test. The following descriptive statistics will be defined for variables with a normal distribution: size, mean value, standard deviation, and 95% confidence interval for the mean value. While size, median, and range will be determined for variables that are not normally distributed.

The Shapiro-Wilk W test with a significance level of  $\alpha=0.05$  will be used to evaluate the normality of distributions.

Principal component analysis (PCA) will assess global relationships between the key variables, regardless of scale. PCA additionally allows the identification of non-obvious and difficult-to-predict correlations between analyzed variables on different measurement scales. The developed PCA model will be estimated using the NIPALS algorithm. The convergence criterion will be set at 0.00001, and the maximum number of iterations will be 100. The number of components will be determined by establishing the maximum predictive ability of  $Q^2$  using V-fold cross-validation, adopting  $V_{max}=7$ . The optimal PCA model will be reduced to principal components, and the results will be presented in a graph, including the contribution of each component to the overall percentage of explained variance and information on their statistical significance.

Pearson correlation coefficient matrices and Spearman's rank correlation coefficients will be calculated to determine correlations between variables of ratio scales.

Their statistical significance will be determined with a t-test adopting a significance level of  $\alpha=0.05$ .

The basis for assessing the correlation of nominal variables will be the significance of Pearson's chi-squared test. In the case of dichotomous variables, for which it will be possible to construct bivariate (2x2) tables, an additional odds ratio (OR) will be determined, along with a 95% confidence interval (OR $\pm$ 95%CI).

A nonparametric Cox proportional hazards model will be used to evaluate the effect of the IPAQ value on survival probability.

The data analysis will also involve testing the statistical significance of differences between mean values: the parametric Student's t-test for independent samples and parametric analysis

of variance (ANOVA) with the post-hoc least significant difference (LSD) test for variables that meet the normality of distribution and homogeneity of variance assumptions, or the nonparametric Mann-Whitney U-test and nonparametric Kruskal-Wallis ANOVA for variables not meeting these assumptions. In addition, Levene's test and the Brown-Forsythe test will assess the homogeneity of variance.

A significance level of  $\alpha=0.05$  will be assumed for all statistical analyses.

Statistical analysis will be performed using StatSoft's Statistica 13.3 PL.

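### Activity-laboratory associations are tested at an unadjusted 5% over an unlisted panel of markers, with no false-discovery control or exploratory label, so their false-positive risk is uncontrolled

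*Combined protocol and SAP*

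**What the plan says.** The outcomes are named in the study plan, in the text after the exclusion criteria. Death from COVID-19, discharge home and ICU transfer are primary. The next group reads "Secondary Outcome Measures: hospitalization length before transfer to intensive care unit, laboratory tests". No individual test is named there.

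The Statistical Analysis Plan (SAP) does not narrow this down. Its ratio-scale variables are "raw MET, hospitalization length, age, BMI, and concentration levels of all biochemical factors studied", so the laboratory panel is open-ended. The SAP then plans the following:

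- **Correlations.** "Pearson correlation coefficient matrices and Spearman's rank correlation coefficients will be calculated to determine correlations between variables of ratio scales". On the coefficients it adds: "Their statistical significance will be determined with a t-test adopting a significance level of" 0.05.
- **Nominal variables.** "The basis for assessing the correlation of nominal variables will be the significance of Pearson's chi-squared test", with odds ratios for 2x2 tables.
- **Group comparisons.** Student's t-test or ANOVA with LSD post-hoc tests, or Mann-Whitney and Kruskal-Wallis where the assumptions fail.
- **PCA.** It is presented partly as a way to bring out unexpected correlations.

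A closing sentence sets 0.05 for every analysis. Activity enters both as raw MET and as a three-level IPAQ category. The SAP does not say which form, or which test, is the one for a given marker.

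**The concern.** A 5% level limits the false-positive risk of one test. Applied separately to every marker in a panel, it does not limit the risk for the panel. Here the panel is a declared secondary outcome, statistical significance is the stated criterion, and nothing tells the reader to treat these results as exploratory. An isolated laboratory marker with p<0.05 could then be reported as a relationship with activity when chance alone would often produce one.

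The open-ended panel adds to this. Without a list of markers and one nominated test for each, a reader of the results cannot tell how many tests lie behind a significant one.

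The point concerns the secondary laboratory family. It would remain if a single primary outcome were named and only one correlation coefficient were used per pair.

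**Working it through.** **The plan's own figure.** The SAP gives no error rate across tests. Its only calculation is the sample size: 1.96² × 0.5 × 0.5 / 0.05² = 384.16, which reproduces its 384. That figure sets the precision of one proportion and has no bearing on how many associations are tested.

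**Inputs.** From the SAP: 0.05 per test. Assumed, because the documents do not give them: two-sided tests; m = 5, 10, 20 or 30 markers; one test of activity per marker; no true association; correlation ρ between any two test statistics from 0 to 0.8.

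**Independent tests.** P(at least one false positive) = 1 − 0.95^m.

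- m = 5: 1 − 0.95⁵ = 0.226
- m = 10: 0.401
- m = 13: 0.487
- m = 14: 0.512, the first value above one half
- m = 20: 0.642
- m = 30: 0.785

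**Correlated tests.** Laboratory markers are correlated, which lowers the risk. For equicorrelated z-statistics with c = 1.96,

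P = 1 − ∫ [Φ((c − √ρ·u)/√(1−ρ)) − Φ((−c − √ρ·u)/√(1−ρ))]^m φ(u) du.

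| Markers | ρ = 0 | ρ = 0.3 | ρ = 0.5 | ρ = 0.7 | ρ = 0.8 | Expected false positives (0.05·m) |
|---|---|---|---|---|---|---|
| 5 | 23% | 21% | 18% | 15% | 13% | 0.25 |
| 10 | 40% | 35% | 29% | 21% | 17% | 0.5 |
| 20 | 64% | 54% | 42% | 29% | 22% | 1.0 |
| 30 | 79% | 66% | 51% | 34% | 26% | 1.5 |

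The expected number does not depend on ρ. Correlation changes only how the false positives cluster.

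**More than one test per marker.** The SAP permits Pearson and Spearman on raw MET, and group tests that could use the IPAQ categories. In 4,000 simulated datasets of 384 patients with no association, and activity cut into thirds to stand in for the IPAQ levels, Pearson or Spearman was significant in 6.0% of datasets. Adding Kruskal-Wallis raised this to 8.8%. At 8.8% per marker, 8 independent markers give 1 − (1 − 0.08825)⁸ = 0.522. The table is therefore conservative if several tests per marker are run and any of them counts.

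**The case against.** **The study is openly looking for relationships.** It is an observational survey with no allocated treatment, and its rationale speaks of searching for associations not yet examined. Many statisticians would accept unadjusted secondary associations if they were reported cautiously. That is a fair argument for a light remedy. It does not remove the point, because the plan never says that these analyses are exploratory and does make significance the criterion.

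**A false finding may not be likely.** A reader might infer that at least one false activity-laboratory association is to be expected. The documents do not support this, because it needs a marker count that they do not give. With ρ = 0.5 the chance is 29%, 42% and 51% for 10, 20 and 30 markers. For 5 independent markers it is 23%. The objection stands: the risk is uncontrolled, not shown to be probable.

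**The full matrix is the wrong denominator.** A matrix of 20 ratio variables has 20 × 19 / 2 = 190 pairs, and it is tempting to quote 190 × 0.05 = 9.5 false positives. But four of the named ratio variables are not laboratory values. With 16 markers, 16 × 15 / 2 = 120 pairs are laboratory-laboratory, many of them truly correlated, and only 16 pair raw MET with a marker. The relevant expectation is 16 × 0.05 = 0.8.

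**Secondary status and intended use.** The study plan does separate primary from secondary outcomes, and nothing says that a laboratory p-value will be presented on a par with a primary result. The SAP simply does not use the separation to order or qualify any test. Likewise, the statement that the findings "can help plan the prevention of this infectious disease and assess the strength of behavioral actions with their impact on the prognosis" concerns activity and the course of the disease. It does not say that laboratory correlations will guide prevention, and it should not be read that way.

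**Conclusion.** The point holds in a limited form. Laboratory tests are an unlisted secondary outcome, each association is tested at an unadjusted 0.05, and there is neither false-discovery control nor an exploratory label. The false-positive risk for activity-laboratory associations is therefore not controlled.

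Over the assumed range of 5 to 30 markers and correlation 0 to 0.8, the chance of at least one false positive runs from 13% to 79%. The lowest value is still over twice the nominal 5%. It exceeds one half from about 14 independent markers at one test each. All these figures assume no true association; the marker counts and correlations are assumptions, not facts about this study.

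The documents do not support saying that a false finding is likely, or that laboratory results will be treated as primary. The matter affects what may be claimed about secondary results, not whether the study can answer its main question. It is a cheap improvement.

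**What to change.** In the SAP, keep the 0.05 level for the primary outcomes (death, discharge home, ICU transfer) and for the other secondary outcome, length of stay before ICU transfer. Qualify the closing sentence on the significance level accordingly, list the markers in the laboratory family before analysis, and add:

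> The activity-laboratory tests, one prespecified test per marker (Spearman correlation with raw MET), form one secondary family. Benjamini-Hochberg adjusted p-values (false discovery rate 5%) will be reported beside raw p-values, and only adjusted p<0.05 will be called significant. Remaining correlations, chi-squared tests and group comparisons that do not involve a primary or named secondary outcome, and the PCA, are exploratory and reported with estimates and intervals where available.

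The restriction in the last sentence matters. A blanket exploratory label on all chi-squared tests and group comparisons would also remove significance claims from the primary outcomes, because the SAP uses those methods for nominal variables such as death and transfer.

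The cost is SAP wording and a short calculation on p-values already planned, with no new data or patients. The downside is that fewer laboratory associations will be called significant. If only one marker has a small p-value, it must be below 0.05/10 = 0.005 in a family of 10, or below 0.05/20 = 0.0025 in a family of 20. The bar is lower when several markers have small p-values.
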